11.3. Data Analysis

Data preparation

Interviews and focus groups will be recorded and transcribed in full by a professional transcription service that has a non-disclosure agreement in place with King's College London. Transcripts will be entered in NVivo 12 for content analysis and will be anonymised at the point of transcription. Care will be taken to ensure that information shared during interviews and focus groups does not contain identifiable data. If an interviewee reveals identifiable data this will be redacted in transcription.

Data coding

Qualitative data will be analysed thematically to explore participants' experiences, views, and perceptions. These will be reflected in a rough coding framework based on the key questions stated at the beginning of this section. The coding framework will also integrate other related issues that emerge during the course of interviews. We will support thematic findings by analysing within cases to develop individual case studies. All qualitative analysis of the interviews will be conducted by at least two members of the team who will identify key themes within each transcript and code their emerging findings independently from each other. After the initial round of independent coding, the researchers will review and discuss emerging themes to check assumptions (and modify the coding framework if needed), and confirm inter-rater reliability. Where diverging opinions occur, these will be discussed, and an agreement reached that is reflected in the final coding framework.

Quantitative analysis will be conducted by analysing administrative data from Greater Change to determine what proportion of people assigned to the treatment group ended up receiving one, and the time delay between assignment to the treatment group; agreement of a budget; funds transferred by Greater Change; and those funds being spent by the charity partner.

Analysis methods

Once all code is reviewed and agreed upon, cross-analysis will be used to identify the reappearance of domains, as well as the categories within each domain.

Table 8: Implementation and Process Evaluation Summary

IPE Research question	Research methodology	Target Population(s)	Data collection methods	Sample size and sampling approach	Analytic Approaches
1, 2, 3, 4, 5, 14	Focus groups, administrative data	Greater Change and charity partner staff	Audio recording and transcription	4 focus groups with 4-5 representatives each First focus groups will consist of exclusively charity partner staff, second will consist of a mix of charity partner and Greater Change staff After conducting these focus groups, we will decide whether the quality of the information is higher when Greater Change employees are present, or not, and use this to inform our strategy.	Thematic analysis, quantitative analysis of administrative data
6, 7, 8, 9, 10, 11, 12, 13	Semi-structure d interviews	PB treatment and control participants	Audio recording and transcription	We are aiming to conduct a total of 20 interviews. We will initially interview 5 participants drawn from the treatment group and 5 from the control group.	Thematic analysis

				We will then review the data and decide how to sample the remaining interviews.	
1, 4, 8	Management information	Organisations, data covering participants in treatment and control group, and caseworkers.	Spreadsheet template completed by charity partners and Greater Change	360 rows in total, each covering a participant in the treatment or control group	Descriptive statistics and inclusion in the complier average causal effects analysis in the impact evaluation.

12. ECONOMIC EVALUATION DESIGN

12.1. Aims, Objectives and Research Questions

Aims

The aim of the economic evaluation is to understand the cost-effectiveness of the personalised budgets intervention, based on the impact evaluation.

- Objectives
 - Understand the costs associated with the Personalised Budgets Intervention.
 - 2. Understand the monetised benefits of the Personalised Budgets Intervention
 - 3. Understand the Cost-Benefit Ratio of the Personalised Budgets Intervention.

12.2. Research Design and Methods

Overall Approach

This economic evaluation will make use of a cost-benefit analysis approach through the use of the Greater Manchester Cost-Benefit Analysis (GMCBA) model according to the latest HTM's Green Book guidance (March 2022). To ensure comprehensive cost identification, we will follow the "ingredients method" (Levin et al., 2018), which promotes detailed accounting of all resources required to implement a program and aligns these costs with the relevant theory of change.

We note that for this CBA to be of maximum relevance for MHCLG, we will strive to align its parameters and assumptions as much as possible with existing cost-benefit analyses conducted by MHCLG.

Information on these assumptions is not available at the time of writing, so this protocol outlines the research team's current assessment. However, if more appropriate assumptions on consensus-based values are identified by MHCLG, these will be utilised for the evaluation. These could be described in a future protocol amendment.

- Relevant Alternatives/ Counterfactuals
 We will be deriving estimates of benefits from the randomised controlled trial impact evaluation, comparing outcomes for the treatment group on average to those in the control group on average.
- Evaluation Perspective and relevant stakeholders
 For this evaluation, we will consider a societal perspective. The stakeholders are therefore:
 - Greater Change
 - Local charity partners
 - Individual participants
 - Local and national governments.

The analysis will aim to incorporate societal factors such as equity considerations, and qualitative impacts on individuals and communities. To achieve this, we will utilise a framework for social cost-benefit analysis (SCBA), which extends cost-benefit analysis by including the full range of costs and benefits, covering social and environmental impacts from the intervention. In SCBA, costs and outcomes, including effectiveness and consequences, are translated into monetary units, allowing both to be expressed in financial terms. The extent to which different societal factors will be considered will depend on data availability and quality.

These benefits will be presented separately from the more direct monetary benefits to programme participants, providing decision-makers with practical insights into expected returns on investment and potential areas of uncertainty.

• Time Horizon

The primary time horizon will be the time horizon of the trial (randomisation + 12 months). Additional exploratory analysis may seek to extend beyond this horizon via extrapolation, in which case we

will apply appropriate discount rates as per the Green Book guidance to future costs and benefits in order to account for the time value of money and ensure comparability across different time periods.

Extension beyond this horizon would allow for a more holistic, and ultimately accurate estimation of the economic benefits and costs associated with respect to the accommodation status of participants. This is particularly important as attainment or retainment of long-term accommodation could imply substantially larger benefits extended into the future.

Costs

As part of the economic evaluation analysis, we will consider costs for the intervention cohort which will include:

- The costs of the personalised budgets themselves, which will be provided by Greater Change to the evaluation team, and which are pre-monetised.
- Staff costs at Greater Change collected from Greater Change utilising a spreadsheet to populate for staff time and associated costs.
- Cost of staff time at charity partners collected from charity partners.

At the local and national level:

- Personalised budget costs will be extrapolated at higher levels utilising homelessness estimates at Local Authority and national level filtered for the percentage of those deemed to be eligible to participate as per their Local Authority characteristics.
- The costs of social/charity workers' staff time will be valued using GMCBA social workers for Adult Services cost per hour estimates at Local Authority level.

Benefits

We will consider both direct and indirect benefits and for the main economic evaluation analysis will assign a monetary value to the benefits accrued for the intervention group compared to business-as-usual. These benefits will include:

At the individual level:

- Improved financial and economic stability, measured through the economic value of employment generated at the individual level compared to business-as-usual. Salary data are not available, therefore the minimum wage will be utilised as a proxy.
- The cost benefits on improved Life Satisfaction, following the Green Book supplementary guidance by measuring in monetary terms the impact on years of total Life Satisfaction.

At the local and national level:

 Reduced use of local services, particularly housing services, captured through the evaluation survey, and monetised using the GMCBA Unit Costs Housing component.³ These are the best available estimates at the time of writing known by the Evaluation team, but we will explore other suitable alternatives with MHCLG and CHI.

³ Retrieved from:

https://www.greatermanchester-ca.gov.uk/what-we-do/research/research-cost-benefit-analysis/

- Reduced fiscal costs of benefits and other economic costs to the exchequer measured through the Employment and Economy element of Units Costs in the GMCBA model. These will include a reduction in costs associated with:
 - Job Seeker's Allowance (JSA)
 - Income Support (IS)
 - Employment and Support Allowance (ESA)

Sensitivity Analyses

Sensitivity analysis will be conducted to test the robustness of results against variations in key parameters and assumptions, addressing uncertainties in data and model inputs.

Optimism Bias Assessment

We will also conduct an Optimism Bias assessment to protect against systematic tendencies to overestimate benefits or underestimate costs. This assessment will attempt to adjust for the following factors:

- Estimates of capital and operating costs, benefit values, and time profiles.
- Provide a more accurate estimate of the probable capital costs and project duration.
- As per Green Book Optimism Bias Supplementary guidance, an adjustment of 10% and 20% of Optimism Bias will be utilised for costs related to the duration of work.

Other costs and benefits associated with this evaluation will be considered and determined based on a shared approach across evaluators working within the CHI Test and Learn programme, in line with CHI's economic evaluation guidance.

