5. IMPACT EVALUATION

5.1. Aims, Objectives and Hypotheses

Aims

This impact evaluation aims to understand the impact that the Greater Change personalised budgets intervention has on housing stability and perceived housing quality and satisfaction, financial stability, subjective wellbeing, life satisfaction, and employment outcomes, measured at baseline, six and twelve months after randomisation using a randomised controlled trial design.

Objectives

Primary objective

The primary objective of the trial is to quantify the effects of providing a personalised budget for financial assistance given to participants who have experience of sleeping rough and are currently housed in temporary accommodation on their housing stability and perceived housing quality and satisfaction.

Secondary objective(s)

The secondary objective is to quantify the impact of the personalised budget intervention on financial stability; wellbeing; life satisfaction; and employment.

Research Hypotheses

Primary hypothesis

Receiving the intervention will:

 Improve housing stability and perceived housing quality and satisfaction

Secondary objective(s)

Receiving the intervention will lead to:

- 2. Improved financial stability
- 3. Improved wellbeing and life satisfaction
- 4. No decrease but perhaps an increase in employment

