Instruments

We will measure this using the Short Warwick Edinburgh Mental Wellbeing Scale as presented in Annex E (Stewart-Brown et al., 2009). The Short Warwick Edinburgh Mental Wellbeing scale is a widely used and validated measure for subjective wellbeing, recommended by the What Works Centre for Wellbeing. It is a 7-item scale with a 1-5 response scale (Ng Fat et al., 2017).

When is it measured?

The outcome measure is collected at the three data collection points - baseline, midline, and endline.

For whom is it measured?
 All participants in the treatment and control groups will be surveyed by IFF.

Life Satisfaction

Definition

Life satisfaction refers to the extent to which respondents feel content and fulfilled with their living conditions. As per the Theory of Change diagram, it is suspected that improved housing and financial security will positively impact life satisfaction.

Instruments

This will be assessed through the first and second items (i.e. life satisfaction and worthwhileness) from the ONS-4 personal wellbeing item battery (see Annex E). Responses will be recorded on an 11-point scale from 0-10.

When is it measured?

The outcome measure is collected at the three data collection points - baseline, midline, and endline.

For whom is it measured?
 All participants in the treatment and control groups will be surveyed by IFF.

Employment

Definition

This will focus on participants' employment status, i.e. whether or not they are engaging in paid work, education or training.

Per the Theory of Change diagram, we suspect that recipients of personalised budgets will be more or equally (but no less) likely to secure or maintain employment.

Instruments

This measure consists of questions which gather information about participants' employment status. It has been developed by CHI and IFF for the purpose of this evaluation (see Annex F), to consistently identify employment outcomes in a way that can be fed into the economic evaluation.

When is it measured?

The outcome measure is collected at the three data collection points - baseline, midline, and endline.

For whom is it measured?

All participants in the treatment and control groups will be surveyed by IFF.

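### If employment rises, the cost-benefit ratio is likely to count part of participants' gain twice, because section 12.2 monetises both earnings and total life satisfaction

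*Protocol*

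**What the plan says.** Section 12.1 sets three objectives for the economic evaluation, the last being "Understand the Cost-Benefit Ratio of the Personalised Budgets Intervention".

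Section 12.2 says that the evaluators "for the main economic evaluation analysis will assign a monetary value to the benefits accrued for the intervention group compared to business-as-usual", and then lists the benefits. Two stand at the individual level:

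- "Improved financial and economic stability, measured through the economic value of employment generated at the individual level compared to business-as-usual". Work is to be priced at the minimum wage, since the trial will hold no information on actual pay.
- "The cost benefits on improved Life Satisfaction, following the Green Book supplementary guidance by measuring in monetary terms the impact on years", where the years are those of life satisfaction in total. No component is carved out.

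Section 7.2 gives the expected route to the second benefit: "it is suspected that improved housing and financial security will positively impact life satisfaction". Annex E measures it with overall ratings of life satisfaction and of how worthwhile life feels.

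On employment, the hypothesis in section 5.1 is "No decrease but perhaps an increase in employment".

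Earlier in section 12.2, after a paragraph on wider social and environmental effects, the protocol adds: "These benefits will be presented separately from the more direct monetary benefits to programme participants". The sensitivity analyses in the same section concern key parameters and assumptions in general terms. Overlap between benefit lines is not mentioned there or under the optimism-bias assessment.

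**The concern.** A person who finds work and rates their life as better because of the income has had one gain. If the wage is entered as one benefit and the whole rise in life satisfaction as another, the part of the rise that is due to the wage enters twice. An overall life-satisfaction rating cannot leave out what a job and its income are worth to the respondent, and section 12.2 does not say that this part will be removed.

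The ratio is a stated objective, and section 12.2 wants the analysis to be of as much use as possible to the funding ministry. If employment improves, the error is upward, and it grows with the share of the life-satisfaction gain that comes through earnings. The issue lies wholly within the two participant-level lines. It is separate from any question about adding wages to saved benefit payments.

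**Working it through.** The protocol gives no benefit total, unit value or ratio, so there is no stated figure to reproduce. The check has three steps.

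**1. Do the lines overlap on the protocol's own account?** Section 12.2 makes earnings the monetary measure of financial stability. Section 7.2 places financial security, together with housing, upstream of life satisfaction. The first line therefore feeds part of the second. The housing route does not pass through earnings, so only part of the life-satisfaction gain is affected.

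**2. Form of the error.** Let E be the monetised earnings gain, L the monetised life-satisfaction gain, m the share of L that runs through earnings, and O all other benefits.

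- Summed benefit: E + L + O
- Benefit without overlap: E + (1 − m)L + O
- Proportional overstatement: mL / (E + (1 − m)L + O)

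With E set to 1 and assumed values for the rest:

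| L/E | m | Overstatement, O = 0 | Overstatement, O/E = 2 |
|---|---|---|---|
| any | 0 | 0% | 0% |
| 0.25 | 0.25 | 5.3% | 2.0% |
| 0.25 | 0.5 | 11.1% | 4.0% |
| 0.25 | 1 | 25.0% | 8.3% |
| 1 | 0.25 | 14.3% | 6.7% |
| 1 | 0.5 | 33.3% | 14.3% |
| 1 | 1 | 100.0% | 33.3% |
| 4 | 0.25 | 25.0% | 16.7% |

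One row worked through: for L/E = 1, m = 0.5 and O/E = 2, the sum is 1 + 1 + 2 = 4.00, the net benefit is 1 + 0.5 + 2 = 3.50, and 4.00/3.50 − 1 = 14.3%. Combinations with mL greater than E are left out. What is counted again is the value of the wage, so the duplicate is taken not to exceed the earnings line. If employment does not change, nothing runs through earnings, so m = 0 and there is no overlap.

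**3. A ceiling in pounds.** The £4,000 average budget is from section 4.1. The employment gain, hours, weeks and wage are assumptions, because the protocol gives none of them.

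- Full-time, full-year earnings: 35 h × 52 weeks × £12 = £21,840
- Gain of 2 points: 0.02 × £21,840 = £437; £437 / £4,000 = 0.11
- Gain of 5 points: 0.05 × £21,840 = £1,092; £1,092 / £4,000 = 0.27
- Gain of 8 points: 0.08 × £21,840 = £1,747; £1,747 / £4,000 = 0.44

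These amounts are the whole earnings line per intervention participant, not an estimate of the overlap. They are loose as a ceiling for three reasons:

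- They take all work as full-time from the day of randomisation. Section 4.1 puts disbursement and spending typically at two to four weeks after referral, section 5.2 allows three months and extensions for spending, and Annex F includes part-time work.
- The denominator leaves out staff costs at the delivery organisation and the charity partners, which section 12.2 counts as costs. With staff costs S per participant, the divisor is £4,000 + S and every increment falls.
- They are reached only if the life-satisfaction gain reflects the earnings in full.

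**The case against.** The strongest reply is that the protocol never writes the sum. Section 12.2 lists benefits, section 12.1 names a ratio without a formula, and some benefits are to be shown separately. Valuation follows government guidance that is not reproduced in the protocol and may deal with overlap. Section 12.2 calls its assumptions a current assessment that may be amended, and an analysis plan could settle how the lines are combined.

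Part of this stands. Summation is implied, not stated, and the content of the cited guidance is unknown here, so it can neither confirm nor cure the problem. But two monetised lines in one main-analysis list, feeding one ratio, are naturally added. The promise of separate presentation follows the passage on wider social and environmental effects and contrasts them with direct monetary benefits to participants. Both disputed lines are listed at the individual level. Even on a generous reading, separate presentation does not say which line enters the ratio. Nor is this only detail left for later: section 12.2 itself chooses the lines and how each is valued.

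A reader might go further and infer that the whole individual-level gain is counted twice, or that the ratio is bound to be too favourable. The protocol does not support either reading. Section 7.2 names housing as well as financial security. Section 7.2 also makes employment a separate outcome, linked to financial stability only by the label on the earnings line in section 12.2. The hypothesis in section 5.1 allows for no change in employment. The overlap takes the sign of the employment effect, so a fall in employment would be double-counted as a harm.

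It is also fair to say that dropping earnings from a headline ratio could undercount, given the societal perspective in section 12.2. Some of the value of earnings may not show in participants' life-satisfaction scores. That is a reason to report both ratios and to justify the headline.

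**Conclusion.** The point holds as a conditional one. Followed as written, the benefit list in section 12.2 is likely to count part of the life-satisfaction gain twice if employment rises, and so to overstate the cost-benefit ratio. Nothing in the protocol removes the overlap.

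The conclusion rests on three conditions: the two lines are summed, employment rises, and some of the life-satisfaction gain comes through earnings. If employment does not change, there is no overlap between these lines.

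The size cannot be derived from the protocol. The range of £437 to £1,747 per intervention participant, or 0.11 to 0.44 on the ratio against a £4,000 budget, is a loose ceiling under the assumed employment gains and full-time, full-year work at £12 an hour. It should not be read as the expected bias. The impact estimates are unaffected.

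**What to change.** Amend section 12.2 in three respects:

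- State that earnings and monetised life satisfaction will not be summed in the same ratio unless the income-related part of the life-satisfaction gain is removed by a stated method.
- Report one ratio with life satisfaction plus public-sector savings, and a second with earnings in place of life satisfaction, described as alternatives. This needs no estimate of the overlapping share.
- Name the headline ratio, with a reason, before treatment labels are opened at endline, so that the more favourable one cannot be chosen afterwards.

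The addendum process in section 13.2 can carry this, and section 12.2 already foresees an amendment on economic assumptions. The cost is a paragraph of text and one extra ratio, with no new data. The headline may be less favourable, and a headline based on life satisfaction may omit some value of earnings that those scores do not reflect.

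### The societal cost-benefit analysis lists both wages gained and state benefits saved, with no deduction for the participant's lost benefits; if the two are summed, a transfer is counted as a gain

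*Protocol*

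**What the plan says.** Protocol section 12.1 sets three objectives for the economic evaluation. The third is a single summary measure: "Understand the Cost-Benefit Ratio of the Personalised Budgets Intervention".

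Section 12.2 fixes the viewpoint: "For this evaluation, we will consider a societal perspective". The stakeholders it then lists include individual participants and also "Local and national governments". The payer and the recipient of state benefits are therefore both inside the boundary of the analysis.

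Under Benefits, section 12.2 gives one list for the main economic analysis, divided by level:

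- **Individual level.** Improved financial and economic stability, "measured through the economic value of employment generated at the individual level compared to business-as-usual". The valuation follows: "Salary data are not available, therefore the minimum wage will be utilised as a proxy".
- **Local and national level.** "Reduced fiscal costs of benefits and other economic costs to the exchequer", taken from the unit costs of the Greater Manchester model, with JSA, Income Support and ESA named.

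Under Costs, section 12.2 lists the personalised budgets and staff time at Greater Change and the charity partners, with the extrapolation of these to local and national level. State benefits that a participant stops receiving appear neither in the cost list nor as a deduction from the wage.

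**The concern.** A benefit payment that ends because someone starts work moves money from the participant to the exchequer. Within a boundary that contains both, it creates nothing. The plan records the exchequer's side of this transfer as a benefit and does not record the participant's side. The wage is already credited to the participant with no stated reduction, so adding the saved payment to it counts the same money once too often.

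What is at stake is the economic ratio that decision-makers would read. Section 12.2 wants the analysis to be of maximum relevance to the funding ministry and to inform expected returns on investment. A ratio near 1 could cross that line because of an accounting choice. The trial's effect estimates on housing and the secondary outcomes are not touched.

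**Working it through.** The protocol states no cost-benefit figure, so there is nothing to reproduce. The check is an accounting identity, followed by a range on assumed inputs.

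**Step 1: the identity.** For one person moved into work, let W be the wage value and B the state benefit no longer paid.

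| Party | Change |
|---|---|
| Participant | W − B |
| Exchequer | + B |
| Society (sum of the two) | W |
| Sum of the two items listed in section 12.2 | W + B |

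The listed items exceed the societal gain by B.

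**Step 2: direction.** The excess scales with the employment effect. If employment rises, the sum is too high by B per person moved into work. If the effect is nil, the excess is nil. If employment falls, W and B are both negative and the sum is too low. Section 5.1 hypothesises no decrease and perhaps an increase.

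**Step 3: inputs for size.** Neither quantity below is in the protocol; both ranges are assumptions.

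- r = B/W, the benefit lost as a share of the wage: 0.1 to 0.5.
- s = the wage value as a share of correctly counted total benefits: 0.1 to 0.6.

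**Step 4: formulas.**

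- Inflation of the employment component: (W + B)/W − 1 = r, so 10% to 50%.
- Inflation of the whole ratio: s × r, because costs are unchanged and total benefits rise from 1 to 1 + s × r.
- Correct ratio when 1.00 is reported: 1/(1 + s × r).

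**Step 5: results.** Each cell gives the inflation of the whole ratio and, in brackets, the correct ratio when 1.00 is reported.

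| | s = 0.1 | s = 0.3 | s = 0.6 |
|---|---|---|---|
| r = 0.1 | 1% (0.99) | 3% (0.97) | 6% (0.94) |
| r = 0.3 | 3% (0.97) | 9% (0.92) | 18% (0.85) |
| r = 0.5 | 5% (0.95) | 15% (0.87) | 30% (0.77) |

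The middle case is 0.3 × 0.3 = 9%, and 1/1.09 = 0.92.

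**The case against.** **The items may not be summed.** No sentence in section 12.2 says that they are. They stand under separate level headings, and the text on perspective says that certain benefits will be shown apart from direct monetary benefits to participants. This stands in part: the error depends on the two items entering the same ratio, and the point must be worded conditionally. But the separate-presentation sentence follows a passage on wider social and environmental impacts. It concerns display and nets nothing. Both items are in one main-analysis list, and section 12.1 names one ratio.

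**The netting rule may lie elsewhere.** Section 12.2 relies on the Greater Manchester model and Treasury guidance, leaves other items to the Centre for Homelessness Impact's guidance, and allows ministry assumptions to replace its own. Netting may therefore happen in practice. The protocol does not state it, and it affirmatively lists both items. The sensitivity analysis varies parameters and assumptions. The only numerical optimism-bias adjustments (10% and 20%) apply to costs related to the duration of work. Neither is stated to remove a double-counted item.

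**The wage may be meant net.** The text does not say gross or full wage. If the employment value were already net of lost benefits, the sum would be correct. However, the stated proxy is the minimum wage, and no deduction is given.

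**Stronger readings that the document does not support.**

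- A reader might infer that students would be credited with a wage, because section 7.2 defines the employment outcome as "whether or not they are engaging in paid work, education or training". But section 12.2 values employment generated, and Annex F codes full-time education separately from paid work and self-employment. No rule assigns a wage to education.
- A reader might add that Universal Credit, named in section 4.1 and Table 5 as support participants may access, is missing from the list of saved benefits, and treat this as a further upward bias. Leaving it out means fewer saved payments are counted, which lowers the total. The list is also not stated to be exhaustive.

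**Conclusion.** The point holds in conditional form. Section 12.2 places payer and recipient in one societal boundary and lists both the minimum-wage value of employment and the saved benefit payments as main-analysis benefits, with no offset for the participant's loss. If these are summed in the single ratio, the transfer is counted as a societal gain.

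A reader might conclude that the ratio is certain to be overstated. The document does not support that: it needs the two items to be summed and the intervention to raise employment.

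The size cannot be computed from the protocol. The ranges of 10-50% for the employment component and about 1-30% for the whole ratio rest entirely on the assumed values of r and s. Only the transfer part of the exchequer item is affected. This is a correction to a supporting economic result and should be made before that analysis is run.

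**What to change.** In section 12.2, state how transfer payments are treated:

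1. In the societal ratio, exclude saved state benefit payments, or keep them and deduct the same amount from participants' gains. Real resource savings, such as administration costs, can stay.
2. Report the saved payments in a separate exchequer-perspective total that excludes participants' wages.
3. Say which of the two totals answers the third objective in section 12.1.

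The cost is a change of protocol wording and one extra summary table. It needs no new data collection. The downside is a less favourable societal ratio if the intervention raises employment.
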